Please note – To calculate the fold increase, result at PII(M3) compared to PRE-for Co-Ad and PIII(M5) compared to
PI(M2) for Control group has to be considered

55

204487 (ZOSTER-059 PRI) Statistical Analysis Plan Amendment 3

Template 35 Listing of potential Immune Mediated Diseases (pIMDs) reported as identified by predefined list of preferred terms and/or by investigator assessment up to end of study by age subgroup <Exposed Set>

Group	Sub.No.	Country	Age strata	Age at onset (Y)	Gender	Race	Primary System Organ Class	Preferred term	Dose	Day of onset	Causality	Serious pIMD based on Investigator?	SAE (Y/N)	Outcome	pIMD Source

Co-Ad = Dose 1: Prevenar 13+ HZ/su, Dose 2: HZ/su

Control = Dose 1: Prevenar 13, Dose 2: HZ/su, Dose 3: HZ/su

50-59YOA = subjects aged 50-59 years; 60-69YOA = subjects aged 60-69 years; ≥70YOA = subjects aged 70 years and over

Template 36 Listing of all SAEs up to end of study by age subgroup < Exposed Set>

Group	Sub. Gender No.	Country	Race	 Age at onset (Year)	Verbatim	term	Primary System Organ Class	MED type	Dose	Day of onset	Duration	Intensity	Causality	Outcome

Co-Ad = Dose 1: Prevenar 13+ HZ/su. Dose 2: HZ/su

Control = Dose 1: Prevenar 13, Dose 2: HZ/su, Dose 3: HZ/su

50-59YOA = subjects aged 50-59 years; 60-69YOA = subjects aged 60-69 years; ≥70YOA = subjects aged 70 years and over

Template 37 Listing of suspected HZ cases from first administered dose up to end of study by age subgroup < Exposed Set >

Group	Sub.	Age strata	Previous dose	Day on-set	Duration	Preferred	AE description	Medical advice	Medically attended visit	Intensity	Causality	Outcome
	No.					term						

Co-Ad = Dose 1: Prevenar 13+ HZ/su, Dose 2: HZ/su

Control = Dose 1: Prevenar 13, Dose 2: HZ/su, Dose 3: HZ/su

50-59YOA = subjects aged 50-59 years; 60-69YOA = subjects aged 60-69 years; ≥70YOA = subjects aged 70 years and over

20-NOV-2019 56

204487 (ZOSTER-059 PRI) Statistical Analysis Plan Amendment 3

Template 38 Listing of (S)AEs and solicited adverse events leading to study or treatment discontinuation <up to month 5><up to end of study> by age subgroup <Exposed Set>

Type of discontinuation: <study/treatment

Group	Subject number	Age strata	Country	AE Description	SAE (Y/N)	Causality	Vaccination and visit
							Vaccination: x at visit x

Co-Ad = Dose 1: Prevenar 13+ HZ/su, Dose 2: HZ/su

Control = Dose 1: Prevenar 13, Dose 2: HZ/su, Dose 3: HZ/su

50-59YOA = subjects aged 50-59 years; 60-69YOA = subjects aged 60-69 years; ≥70YOA = subjects aged 70 years and over

Template 39 Maximum intensity of solicited <local, general> adverse event ongoing beyond the 7-day (Days 1-7) post-vaccination period following each dose and overall <Exposed Set>

			Time to resolution	<each group> Value or</each 	<each group> Value or</each
Dose	Adverse event	Туре	(days)	n	n
<each dose=""></each>	<each adverse<="" td="">All	N	XX	XX	</each>	All	N	XX	XX
	event>		n	xx	XX
			q1	XX.X	XX.X
			median	XX.X	XX.X
			q3	XX.X	XX.X
		Grade 3	N	XX	XX
			n	XX	XX
			q1	XX.X	XX.X
			median	XX.X	XX.X
			q3	XX.X	XX.X
		Grade 3*Related	N	XX	XX
			n	xx	xx
			q1	XX.X	XX.X
DVERALL/DOSE			median	xx.x	XX.X
			q3	XX.X	XX.X
OVERALL/DOSE	<each adverse="" event<="" td="">><each type=""></each>	N	XX	XX	</each>	> <each type=""></each>	N	XX	XX
			n	XX	XX
			q1	XX.X	XX.X
			median	XX.X	XX.X
OVERALL/DOSE			q3	XX.X	XX.X

Co-Ad = Dose 1: Prevenar 13+ HZ/su, Dose 2: HZ/su

Control = Dose 1: Prevenar 13, Dose 2: HZ/su, Dose 3: HZ/su

Time to resolution: number of days beyond the end of the follow-up period N = number of adverse events that were ongoing after the follow-up period

n = number of adverse events that were ongoing after the follow-up period with a complete end date

q1 = 25th percentile; q3= 75th percentile

204487 (ZOSTER-059 PRI) Statistical Analysis Plan Amendment 3

Template 40 Number and percentage of doses reporting the occurrence of <grade 3> unsolicited adverse events classified by MedDRA Primary System Organ Class and Preferred Term <with causal relationship to vaccination> within the 30-day (Days 1-30) post-vaccination period <Exposed Set>

			ach I =	gr	oup
					5% CI
Primary System Organ Class (CODE)	Preferred Term (CODE)	n	%	LL	UL
At least one adverse event					
Gastrointestinal disorders (10017947)	Diarrhoea (10012735)				
, ,	Teething (10043183)				
	Vomiting (10047700)				
General disorders and administration site conditions (10018065)	Pyrexia (10037660)				
Immune system disorders (10021428)	Seasonal allergy (10048908)				
Infections and infestations (10021881)	Conjunctivitis (10010741)				
, ,	Otitis media (10033078)				
	Paronychia (10034016)				
	Tonsillitis (10044008)				
	Tonsillitis streptococcal (10044013)				
	Viral upper respiratory tract infection				
	(10047482)				
Injury, poisoning and procedural complications (10022117)	Arthropod bite (10003399)				
,	Face injury (10050392)				
	Head injury (10019196)				
Skin and subcutaneous tissue disorders (10040785)	Miliaria (10027627)				

Co-Ad = Dose 1: Prevenar 13+ HZ/su, Dose 2: HZ/su

Control = Dose 1: Prevenar 13, Dose 2: HZ/su, Dose 3: HZ/su

At least one adverse event = at least one adverse event experienced (regardless of the MedDRA Preferred Term) N = number of administered doses

n/% = number/percentage of doses followed by the adverse event

95% CI = exact 95% confidence interval; LL = Lower Limit, UL = Upper Limit

204487 (ZOSTER-059 PRI) Statistical Analysis Plan Amendment 3

Template 41 Number and percentage of subjects reporting the occurrence of <serious adverse events, potential Immune Mediated Disease> classified by MedDRA Primary System Organ Class and Preferred Term from <first vaccination up to 30 days post last vaccination, from 30 days post last vaccination dose up to end of study, from first vaccination up to study end> <,including number of events><Exposed Set>

			(-Ad =			(trol =
				95% CI					95% CI	
Primary System Organ Class (CODE)	Preferred Term (CODE)	n*	n	%	LL	UL	n*	n ^c	% L	L UL
At least one adverse event										
Blood and lymphatic system disorders (10005329)	Leukocytosis (10024378)									
Cardiac disorders (10007541)	Acute myocardial infarction (10000891)									
	Atrial fibrillation (10003658)									
	Cardiac failure congestive									
	(10007559)									
	Tachycardia (10043071)									
	Ventricular tachycardia (10047302)									

Co-Ad = Dose 1: Prevenar 13+ HZ/su, Dose 2: HZ/su

Control = Dose 1: Prevenar 13, Dose 2: HZ/su, Dose 3: HZ/su

At least one adverse event = at least one adverse event experienced (regardless of the MedDRA Preferred Term)

N = number of subjects included in the considered cohort in each group

n/% = number/percentage of subjects reporting the adverse event at least once

n* = **n**umber of events reported

95% CI = exact 95% confidence interval; LL = Lower Limit, UL = Upper Limit

Please note that n* will be used to present pIMD for CTRS posting.

Template 42 Global Summary of <serious adverse events, potential Immune
Mediated Disease> <with causal relationship with vaccination>
reported from <first vaccination up to 30 days post last vaccination,
from 30 days post last vaccination dose up to end of study, from
first vaccination up to study end> <Exposed Set>

	Co-Ad	Control	Total
Number of subjects with at least one <sae, pimd=""> reported</sae,>			
Number of doses followed by at least one <sae, pimd=""></sae,>			
Number of <sae, pimd=""> classified by MedDRA Preferred Term*</sae,>			
Number of <sae, pimd=""> reported**</sae,>			

Co-Ad = Dose 1: Prevenar 13 + HZ/su, Dose 2: HZ/su

Control = Dose 1: Prevenar 13, Dose 2: HZ/su, Dose 3: HZ/su

N = number of subjects included in the considered cohort in each group

^{*} Adverse events reported by a subject after a given dose and classified by the same Preferred Term are counted once
** Adverse events reported by a subject after a given dose and classified by the same Preferred Term and the same
start date of the event, are counted once

204487 (ZOSTER-059 PRI) Statistical Analysis Plan Amendment 3

Template 43 Vaccine response rates for anti-gE antibody concentrations at one month post dose 2 of HZ/su vaccine <PPS for immunogenicity, Exposed Set>

			•	<each gro<="" th="">up>		</each>	up>	
					95	5% CI
A (2) . 1	Pre-vaccination	N.		0/		
Antibody	status	N	n	%	LL	UL
<each antibody=""></each>	S-	XXXX	XXXX	XX.X	XXX.X	XXX.X
•	S+	XXXX	XXXX	XX.X	XXX.X	XXX.X
	Total	XXXX	XXXX	XX.X	XXX.X	XXX.X

Co-Ad = Dose 1: Prevenar 13+ HZ/su, Dose 2: HZ/su

Control = Dose 1: Prevenar 13, Dose 2: HZ/su, Dose 3: HZ/su

S-= seronegative subjects (antibody <concentration> < <cut off> <unit>) at pre-vaccination; S+ = seropositive subjects (antibody <concentration>≥ <cut off> <unit>) at pre-vaccination

Total = subjects either seropositive or seronegative at pre-vaccination

Vaccine response defined as:

For initially seronegative subjects, antibody concentration at post-vaccination ≥ 4 fold the cut-off for Anti-gE (4x97 mIU/ml)

For initially seropositive subjects, antibody concentration at post-vaccination ≥ 4 fold the pre-vaccination antibody concentration

N = number of subjects with both pre- and post-vaccination results available

[figure not shown]
n/% = number/percentage of responders

<95>% CI = exact <95>% confidence interval, LL = Lower Limit, UL = Upper Limit

Please note – To calculate the vaccine response, result at PII(M3) compared to PRE-for Co-Ad and PIII(M5) compared to PI(M2) for Control group has to be considered

204487 (ZOSTER-059 PRI) Statistical Analysis Plan Amendment 3

Template 44 Reverse cumulative distribution curves for <anti-gE antibody concentration, anti-pneumococcal <X> antibody titres> in each group at baseline and <post dose 2 of HZ/su vaccine, post dose of Prevenar 13> <PPS for immunogenicity, Exposed Set>

Co-Ad = Dose 1: Prevenar 13+ HZ/su, Dose 2: HZ/su

Control = Dose 1: Prevenar 13, Dose 2: HZ/su, Dose 3: HZ/su

Note: This graph is provided as an example. The same graph will be provided in colour for each time point and each assay comparing the values of the groups

Please note to consider PRE and PI(M1) for both group for pneumococcal antibody. For gE antibody, PRE and PII(M3) for Co-Ad and PI(M2) and PIII(M5) for Control group.

204487 (ZOSTER-059 PRI) Statistical Analysis Plan Amendment 3

Template 45 Number and percentage of subjects <with><experiencing> fatal SAEs classified by MedDRA Primary System Organ Class and Preferred Term <who died><with onset of fatal SAE> <during the period starting> <from first vaccination up to 30 days post last vaccination dose> <after 30 days post last vaccination dose up to study end><from first vaccination until the study end><during the entire study period> <Exposed Set>

			_	o-A N =				ontr N =	trol =		
				95% CI				ć	95% CI		
Primary System Organ Class (CODE)	Preferred Term (CODE)	n	%	LL	UL	n	%	LL	UL		
At least one adverse event											
Blood and lymphatic system disorders (10005329)	Leukocytosis (10024378)										
Cardiac disorders (10007541)	Acute myocardial infarction (10000891)										
	Atrial fibrillation (10003658)										
	Cardiac failure congestive										
	(10007559)										
	Tachycardia (10043071)										
	Ventricular tachycardia (10047302)										

Co-Ad = Dose 1: Prevenar 13+ HZ/su. Dose 2: HZ/su

Control = Dose 1: Prevenar 13. Dose 2: HZ/su. Dose 3: HZ/su

At least one adverse event = at least one adverse event experienced (regardless of the MedDRA Preferred Term)

N = number of subjects included in the considered cohort in each group

n/% = number/percentage of subjects reporting the adverse event at least once

95% CI = exact 95% confidence interval; LL = Lower Limit, UL = Upper Limit

Template 46 Summary of subject disposition from Enrolled Set to Randomized Set

	Total N=XXX n %
Number of subjects who signed an informed consent	
Withdrawals prior to randomization	XXX XX.X
<withdrawal 1="" reason=""></withdrawal>	xxx xx.x
<withdrawal 2="" reason=""></withdrawal>	xxx xx.x
	xxx xx.x
	xxx xx.x
Number of subjects included in Randomized Set	

N = **n**umber of subjects

n% = number / percentage of subjects in a given category

204487 (ZOSTER-059 PRI) Statistical Analysis Plan Amendment 3

Template 47 Summary of subject disposition from Randomized Set to Per Protocol Set

	<group 1=""></group>	<group 2=""></group>	Total
	N=XXX	N=XXX	N=XXX
	n %	n %	n %
Number of subjects			
included in Randomized Set			
Withdrawals	XXX XX.X	XXX XX.X	XXX XX.X
<withdrawal 1="" reason=""></withdrawal>	XXX XX.X	xxx xx.x	xxx xx.x
<withdrawal 2="" reason=""></withdrawal>	XXX XX.X	xxx xx.x	xxx xx.x
Eliminations	xxx xx.x	xxx xx.x	xxx xx.x
<elimination 1<="" reason="" td="">xxx xx.x	xxx xx.x	xxx xx.x	</elimination>	xxx xx.x	xxx xx.x	xxx xx.x
(code)>	xxx xx.x	xxx xx.x	xxx xx.x
<elimination 2<="" reason="" td="">			</elimination>			
(code)>			
	xxx xx.x	xxx xx.x	xxx xx.x
Number of subjects			
included in Exposed Set			
Elimination 1			
Number of subjects			
included in PPS for			
immunogenicity			

Co-Ad = Dose 1: Prevenar 13+ HZ/su, Dose 2: HZ/su

Control = Dose 1: Prevenar 13, Dose 2: HZ/su, Dose 3: HZ/su

N = number of subjects

n% = number / percentage of subjects in a given category

204487 (ZOSTER-059 PRI) Statistical Analysis Plan Amendment 3

Template 48 Listing of subjects who died during the entire study period and their fatal SAEs by age subgroup < Enrolled Set>

	No.	Sex	Country	strata	Age at Onset (Year)	Verbatim	Preferred term	,	type	prior to onset of fatal SAE	between onset of	prior to death	,	SAE Duration	SAE Causality
No Group	PPD									0	-	0	-		
										0	-	0	-		
										1	XX	1	XX		
										1	XX	2	XX		
										1	XX	1	XX		
										1	XX	1	XX		

Co-Ad = Dose 1: Prevenar 13+ HZ/su, Dose 2: HZ/su

Control = Dose 1: Prevenar 13, Dose 2: HZ/su, Dose 3: HZ/su

No Group= Enrolled not vaccinated

50-59YOA = subjects aged 50-59 years; 60-69YOA = subjects aged 60-69 years; ≥70YOA = subjects aged 70 years and over

MED = Medical Advice type (HO: hospitalisation, ER: emergency room visit, MD: medical practice visit)

20-NOV-2019 64

204487 (ZOSTER-059 PRI) Statistical Analysis Plan Amendment 3

Template 49 Summary of subjects by unsolicited adverse event category, with onset within 30 days of each vaccination

		<gro N=X</gro 	up 1> XXX			iroup 2 =XXXX		
	•		95%	6 CI			95%	% CI
	n	%	LL	UL	n	%	LL	UL
At least one unsolicited adverse event	XXX	XX.X	XX.X	XX.X	XXX	XX.X	XX.X	XX.X
At least one grade 3 unsolicited adverse event	xxx	xx.x	xx.x	xx.x	XXX	XX.X	xx.x	xx.x
At least one related unsolicited adverse event	ххх	XX.X	XX.X	XX.X	XXX	XX.X	XX.X	XX.X
At least one grade 3 related unsolicited adverse event	ххх	XX.X	XX.X	XX.X	XXX	XX.X	XX.X	XX.X

Co-Ad = Dose 1: Prevenar 13+ HZ/su, Dose 2: HZ/su

Control = Dose 1: Prevenar 13, Dose 2: HZ/su, Dose 3: HZ/su

N = number of subjects included in the considered cohort in each group

n/% = number/percentage of subjects reporting the adverse event at least once 95% CI = exact 95% confidence interval; LL = Lower Limit, UL = Upper Limit

Template 50 Summary of subjects by serious adverse event and potential Immune Mediated Disease categories, with onset <from first vaccination to 30 days post last vaccination, after 30 days post last vaccination until study end>

			•		iroup 2		>	
	N=X	XXX		N=XXXX				
		95%	6 CI			95% CI		
n	%	LL	UL	n	%	LL	UL	
XXX	xx.x	XX.X	XX.X	XXX	XX.X	XX.X	XX.X	
XXX	xx.x	xx.x	xx.x	XXX	XX.X	xx.x	xx.x	
XXX	XX.X	XX.X	XX.X	XXX	XX.X	XX.X	XX.X	
XXX	XX.X	XX.X	XX.X	XXX	xx.x	XX.X	XX.X	
	XXX XXX	n % xxx xx.x xxx xx.x xxx xx.x	n % LL xxx xx.x xx.x xx.x xxx xx.x xx.x x	95% CI	95% CI n % LL UL n xxx xx.x xx.x xx.x xx.x xxx xxx xx.x xx.x xx.x xx.x xxx xxx xx.x xx.x xx.x xx.x xxx	95% CI n % LL UL n % xxx xx.x xx.x xx.x xx.x xx.x xx.x xx	95% CI 95% n % LL UL n % LL xxx xx.x xx.x xx.x xx.x xx.x xx.x x	

Co-Ad = Dose 1: Prevenar 13+ HZ/su, Dose 2: HZ/su

Control = Dose 1: Prevenar 13, Dose 2: HZ/su, Dose 3: HZ/su

N = number of subjects included in the considered cohort in each group

n/% = number/percentage of subjects reporting the adverse event at least once

95% CI = exact 95% confidence interval; LL = Lower Limit, UL = Upper Limit

204487 (ZOSTER-059 PRI) Statistical Analysis Plan Amendment 2

	Statistical Analysis Flatt Americanent 2
GlaxoSmithKline	Statistical Analysis Plan
Detailed Title:	A Phase IIIB, randomized, open-label, multicenter clinical trial to assess the immunogenicity and safety of GSK Biologicals' Herpes Zoster vaccine GSK1437173A when co-administered with Prevenar13 in adults aged 50 years and older.
eTrack study number and Abbreviated Title	204487 (ZOSTER-059 PRI)
Scope:	All analyses planned per protocol.
Date of Statistical Analysis Plan	Amendment 2 Final: 20 November 2019

APP 9000058193 Statistical Analysis Plan Template V4 (Effective date: 3 June 2019)

204487 (ZOSTER-059 PRI) Statistical Analysis Plan Amendment 2

TABLE OF CONTENTS

				PAGE
LIS	T OF A	BBREVIA	ΓΙΟΝS	10
1.	DOCU	JMENT HIS	STORY	12
2.	STUD	Y DESIGN	l	13
3.	OR IE	CTIVES		15
٥.	3.1.		ıry objectives	
	3.2.		ry objective	
4.	ENDF	OINTS		16
	4.1.		endpoints	
	4.2.	Secondar	ry endpoints	16
5.	ANAL	YSIS SETS	3	17
	5.1.			
		5.1.1.	Enrolled Set	
			Randomized Set	
		5.1.3.	Exposed Set (ES)*	

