10.5.1. Handling of missing data

For the analysis of solicited symptoms, missing or non-evaluable measurements will not be imputed. Therefore, the analysis of the solicited symptoms based on the TVC will include only subjects/doses with documented safety data (i.e. symptom screen completed).

For the analysis of unsolicited AEs/SAEs/pIMDs/concomitant medication, all vaccinated subjects will be considered and subjects who did not report an event will be considered as subjects without an event.

For a given subject and a given immunogenicity measurement, missing or non-evaluable measurements will not be replaced. Therefore, a subject will be excluded from an analysis if all measurements are missing or non-evaluable.

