12.1.3. Safety

For a given subject and the analysis of solicited adverse event during the 7 day follow-up period after vaccination, missing or non-evaluable measurements will not be replaced. Therefore, the analysis of the solicited adverse events based on the ES will include only vaccinated subjects with documented safety data (i.e., symptom screen completed). More specifically the following rules will be used:

- Subjects who documented the absence of a solicited adverse event after one dose will be considered not having that adverse event after that dose.
- Subjects who documented the presence of a solicited adverse event and fully or
 partially recorded daily measurement over the solicited period will be included in the
 summaries at that dose and classified according to their maximum observed daily
 recording over the solicited period.

204487 (ZOSTER-059 PRI) Statistical Analysis Plan Amendment 3

- Subjects who documented the presence of a solicited adverse event after one dose
 without having recorded any daily measurement will be assigned to the lowest
 intensity category at that dose (i.e., 38°C for fever or grade 1 for other adverse
 events). The subject will only be presented in the subject with adverse event
 experienced and not in specific grade information.
- Doses without adverse event sheets documented will be excluded.

For analysis of unsolicited AEs, such as SAEs or adverse events by MedDRA Primary SOC and PTs term, and for the analysis of concomitant medications, all vaccinated subjects will be considered. Subjects who did not report the event or the concomitant medication will be considered as subjects without the event or the concomitant medication respectively.

Associated dose: The associated dose for an event (e.g., AE, medication, vaccination,...) is the study dose given before an event. In case the event takes place on a day a study dose is given, the associated dose will be that of the study dose even if the event actually took place before. For instance, for a conc. medication started on the day of study dose 2 but before dose 2 administrations, the associated dose will be dose 2

The way the percentage of subjects will be derived will depend on the event analysed (see the following table for details). As a result, the denominator (N) will differ from one table to another.

Event	N used for deriving %	Terminology used in the tables for N
Concomitant	All vaccinated subjects	Number of subjects with at least one

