medication		administered dose
Solicited local	All vaccinated subjects with at least one	For each dose and overall/subject:
adverse event	solicited local adverse event	N= number of subjects with at least one
	documented as either present or absent	documented dose
		For overall/dose:
		N= number of documented doses
Solicited general	All vaccinated subjects with at least one	For each dose and overall/subject:
adverse event	solicited general adverse event	N= number of subjects with at least one
	documented as either present or absent	documented dose
		For overall/dose:
		N= number of documented doses
Unsolicited adverse	All vaccinated subjects	Number of subjects with at least one
event from day 0 to		administered dose
day X		
SAE	All vaccinated subjects	Number of subjects with at least one
		administered dose

- The maximum intensity of local injection site redness and swelling will be scored at GSK Biologicals as follows:
 - 0 : <20 mm
 - 1 : > 20 mm to < 50 mm diameter
 - 2: > 50 mm to \leq 100 mm diameter
 - 3 : > 100 mm diameter

204487 (ZOSTER-059 PRI) Statistical Analysis Plan Amendment 3

Fever is defined as temperature $\geq 38.0 \text{ C} / 100.4 \text{ F}$ for oral, axillary, tympanic or rectal route. The preferred route for recording temperature in this study will be oral. For the analysis, temperatures will be coded as follows:

Grade	Temperature (oral, axillary, tympanic or rectal route)	
0	< 38°C	
1	≥ 38°C - ≤ 38.5°C	
2	> 38.5°C - ≤ 39°C	
3	> 39°C	

• Conversion of temperature to °C -

The following conversion rule is used for the conversion of temperature to °C

Temperature in °Celsius = ((Temperature in °Fahrenheit -32) *5)/9

The result is rounded to 1 decimal digit.

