	Local adverse events										
Overall/dose	Any adverse event										
	General adverse events										
	Local adverse events										
Overall/subject	Any adverse event										
•	General adverse events										
	Local adverse events										

Co-Ad = Dose 1: Prevenar 13+ HZ/su, Dose 2: HZ/su

Control = Dose 1: Prevenar 13, Dose 2: HZ/su, Dose 3: HZ/su

For each dose and overall/subject: N = number of subjects with at least one documented dose; n/% =

number/percentage of subjects presenting at least one type of adverse event

For overall/dose: N = number of documented doses; n/% = number/percentage of doses followed by at least one type of adverse event

95% CI = exact 95% confidence interval, LL = Lower Limit, UL = Upper Limit

204487 (ZOSTER-059 PRI) Statistical Analysis Plan Amendment 3

Template 17 Incidence of solicited local adverse events reported during the 7-day (Days 1-7) post-vaccination period by study vaccine following each dose and overall <Exposed Set>

						Co-A	d			(Contr	ol	
							95%	6 CI				95%	% CI
Dose	Adverse event	Product	Туре	N	n	%	LL	UL	N	n	%	LL	UL
Dose 1	Pain	HZ/su	All										
			Grade 2 or 3										
			Grade 3										
			Medical advice										
		Prevenar13	All										
			Grade 2 or 3										
			Grade 3										
			Medical advice										
	Redness (mm)	HZ/su	All										
	, ,		>50										
			>100										
			Medical advice										
		Prevenar 13	All										
			>50										
			>100										
			Medical advice										
	Swelling (mm)	HZ/su	All										
			>50										
			>100										
			Medical advice										
		Prevenar 13	All										
			>50										
			>100										
			Medical advice										
Dose 2													
Dose 3													
Overall/Dose													
Overall/Subject													
	Drayonar 12 - H7/	D 0 117	1.										

Co-Ad = Dose 1: Prevenar 13+ HZ/su, Dose 2: HZ/su

Control = Dose 1: Prevenar 13, Dose 2: HZ/su, Dose 3: HZ/su

For each dose: N = number of subjects with the corresponding documented dose; n/% = number/percentage of subjects reporting the type of adverse event at least once following the corresponding dose

For Overall/dose: N = number of documented dose; n/% = number/percentage of doses followed by at least one type of adverse event

For Overall/subject: N = number of subjects with at least one documented dose; n/% = number/percentage of subjects reporting the type of adverse event at least once

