		>36.5											
			>37.0										
			>37.5										
			>38.0										
			>38.5										
			>39.0										
			>39.5										
			>40.0										
Dose 2	Temperature (°C)	Oral	≥35.0										
			>35.5										
			>36.0										
			>36.5										
			>37.0										
			>37.5										
			>38.0										
			>38.5										
			>39.0										
			>39.5										
			>40.0										
Dose 3			10.0		t	1	1					1	

Co-Ad = Dose 1: Prevenar 13+ HZ/su, Dose 2: HZ/su

Control = Dose 1: Prevenar 13, Dose 2: HZ/su, Dose 3: HZ/su

For each dose: N = number of subjects with at least one documented dose; n/% = number/percentage of subjects

reporting the temperature at least once

95%CI = Exact 95% confidence interval; LL = lower limit, UL = upper limit

204487 (ZOSTER-059 PRI) Statistical Analysis Plan Amendment 3

Template 20 Number and percentage of subjects reporting the occurrence of <grade 3> <non-serious> unsolicited adverse events classified by MedDRA Primary System Organ Class and Preferred Term <with causal relationship to vaccination, with medically attended visit>, within the 30-day (Days 1-30) post-vaccination period <,including numbers of events><Exposed Set>

		Ea N		gro	oup	
						5% CI
Primary System Organ Class (CODE)	SOC Diarrhoea (10012735) Teething (10043183) Vomiting (10047700) At least one PT related to the corresponding SOC Pyrexia (10037660) Seasonal allergy (10048908) Conjunctivitis (10010741) Otitis media (10033078) Paronychia (10034016)	n*	n	%	LL	UL
	At least one adverse event					
Gastrointestinal disorders (10017947)	At least one PT related to the corresponding SOC					
	Diarrhoea (10012735)					
	Teething (10043183)					
General disorders and administration site conditions	At least one PT related to the corresponding					
(10018065)	SOC					
	Pyrexia (10037660)					
Immune system disorders (10021428)	, , , , , , , , , , , , , , , , , , , ,					
Infections and infestations (10021881)	Conjunctivitis (10010741)					
	Otitis media (10033078)					
	Paronychia (10034016)					
	Tonsillitis (10044008)					
	Tonsillitis streptococcal (10044013)					
	Viral upper respiratory tract infection (10047482)					
Injury, poisoning and procedural complications (10022117)	Arthropod bite (10003399)					
,	Face injury (10050392)					
	Head injury (10019196)					
Skin and subcutaneous tissue disorders (10040785)	Miliaria (10027627)					

Co-Ad = Dose 1: Prevenar 13+ HZ/su, Dose 2: HZ/su

Control = Dose 1: Prevenar 13, Dose 2: HZ/su, Dose 3: HZ/su

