For each dose: N = number of subjects with the corresponding documented dose; n/% = number/percentage of subjects reporting the type of adverse event at least once following the corresponding dose

For Across dose: N = number of subjects with at least one documented dose; n/% = number/percentage of subjects reporting the adverse event at least once

95%CI= Exact 95% confidence interval; LL = lower limit, UL = upper limit

204487 (ZOSTER-059 PRI) Statistical Analysis Plan Amendment 3

Template 27 Number (%) of subjects reported solicited general adverse events during the 7-day (Days 1-7) post-vaccination period following each dose and across dose <Exposed Set>

					<each gr<="" th="">oup>		</each>	oup>	
						9:	5 % CI
Dose	Adverse event	Туре	N	n	%	LL	UL
Dose 1	Fatigue	All					
		Grade 3					
		Related					
	Gastrointestinal symptoms	All					
		Grade 3					
		Related					
	Headache	All					
		Grade 3					
		Related					
	Myalgia	All					
	, ,	Grade 3					
		Related					
	Shivering	All					
		Grade 3					
		Related					
	Fever (Oral) (°C)	All (≥38.0)					
		>39.0					
		Related					
Dose 2	Fatigue						
	Gastrointestinal symptoms						
	Headache						
	Myalgia						
	Shivering						
	Fever (Oral) (°C)						
Across Dose							

<each group>:

Co-Ad = Dose 1: Prevenar 13+ HZ/su, Dose 2: HZ/su

Control = Dose 1: Prevenar 13, Dose 2: HZ/su, Dose 3: HZ/su

For each dose: N = number of subjects with the corresponding documented dose; n/% = number/percentage of subjects reporting the adverse event at least once following the corresponding dose

For Across dose: N = number of subjects with at least one documented dose; n/% = number/percentage of subjects reporting the adverse event at least once

95%CI= Exact 95% confidence interval; LL = lower limit, UL = upper limit

204487 (ZOSTER-059 PRI) Statistical Analysis Plan Amendment 3

Template 28 Number and percentage of subjects with <anti-pneumococcal <X> antibody titres> equal to or above <cut-off> and GMT <PPS for immunogenicity, Exposed Set>

				<	≥each LL	serot OQ>	ype		<gm-</gm	Γ>		
						95	% CI		9	95% CI		
Antibody	Group	Timing	N	n	%	LL	UL	value	LL	UL	Min	Max
<anti-< td="">Co-Ad	PRE											</anti-<>	Co-Ad	PRE										
pneumococcal <x> antibody></x>		PI(M1) or PII(M3)										
	Control	PRE or PI(M2)										
		PI(M1) or PIII(M5)										

<each group>:

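### The SAP 12.1.3 denominator table and Templates 16 and 19 define the per-dose N as subjects with any documented dose, which conflicts with the SAP's own exclusion rule and, read literally, would dilute Dose 2 and Dose 3 rates

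*SAP*

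**What the plan says.** SAP Amendment 3 carries two definitions of the denominator for a per-dose row of solicited events.

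The broad definition counts anyone with a sheet for any dose. It stands in three places:

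- SAP 12.1.3, denominator table, rows for solicited local and solicited general events. A single entry headed "For each dose and overall/subject" begins "N= number of subjects with at least one" and runs on, over a line break in the cell, to a documented dose.
- Template 16 (any, general and local events by dose): "For each dose and overall/subject: N = number of subjects with at least one documented dose".
- Template 19 (temperature by route): "For each dose: N = number of subjects with at least one documented dose".

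The dose-specific definition stands in four templates. Templates 17 and 18 say "For each dose: N = number of subjects with the corresponding documented dose". Templates 26 and 27 say "N = number of subjects with the corresponding documented dose". All four keep the broad definition for the overall/subject or across-dose rows only.

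Two rules in the running text bear on the choice. SAP 12.1.3 states: "Doses without adverse event sheets documented will be excluded". Protocol 10.5.1 says that the analysis of solicited symptoms "will include only subjects/doses with documented safety data (i.e. symptom screen completed".

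**The concern.** Under the broad definition, a subject who returned only a Dose 1 sheet stays in the Dose 2 and Dose 3 denominators and adds nothing to the numerator. That subject is counted as event-free after a dose that was not given or not documented.

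The plan foresees such subjects. Protocol 9.2.2 lists solicited and serious adverse events among the reasons for stopping vaccination. Someone who stopped because of a reaction to one dose would then lower the displayed rate for the next.

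The main output at stake is Template 16. It delivers the first tabulation promised in SAP 6.4.1 and serves the only secondary objective, safety and reactogenicity. Its numerator wording also does not tie the event to the dose in the row, as the footnotes of Templates 17 and 18 do.

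**Working it through.** **1. Which definition fits the plan's own rules.**

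| Place | Who is in N for a Dose k row |
|---|---|
| SAP 12.1.3 table; Templates 16 and 19 | anyone with a sheet for any dose |
| Templates 17, 18, 26, 27 | those with a sheet for Dose k |
| SAP 12.1.3 text; protocol 10.5.1 | undocumented doses left out |

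A subject cannot be left out for Dose 2 and also be counted in the Dose 2 denominator. The text rules agree with the second row and contradict the first, so SAP 12.1.3 conflicts with itself as well as with the four templates.

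**2. Effect of the broad definition.** Let n_k be the subjects with Dose k documented, N_any the subjects with any dose documented, and r the rate among the n_k. Then

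shown rate = r × n_k / N_any, and relative understatement = 1 − n_k / N_any.

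**3. Inputs available.** The documents state no reactogenicity rate, diary-return rate or per-dose attrition. The nearest figure is in protocol 10.3: about 10% non-evaluable, which takes 410 evaluable subjects to 456 enrolled per group. It reproduces: 410 / 0.90 = 455.6, rounded up to 456. That allowance covers evaluability in the sample-size calculation for the immunogenicity objectives, not missing diaries, so it serves here only as an illustrative ceiling. The rates below are assumed too.

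**4. Numbers.** With m the share of later-dose sheets missing, n_k / N_any = 1 − m.

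| m (assumed) | r = 10% | r = 60% | r = 80% |
|---|---|---|---|
| 0% | 10.0% | 60.0% | 80.0% |
| 2% | 9.8% | 0.60 × 0.98 = 58.8% | 78.4% |
| 5% | 9.5% | 0.60 × 0.95 = 57.0% | 76.0% |
| 10% | 9.0% | 0.60 × 0.90 = 54.0% | 72.0% |

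**5. Dose 3 in Co-Ad.** The group definitions in SAP 11 give Co-Ad two study doses and Control three. For Co-Ad n_3 = 0, so a literal Template 16 prints a Dose 3 row with N close to the whole arm and 0% events. The row means nothing.

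**6. Where the two definitions meet the same quantity.** Template 16 reports aggregates, while Templates 17 and 18 report individual events, so their percentages are not directly comparable. The clear overlap is oral temperature: Templates 18 and 19 both show the cumulative thresholds from above 38.0°C to above 40.0°C by dose.

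**7. The combined version of Template 16.** This template is also used for solicited and unsolicited events together. For unsolicited events, protocol 10.5.1 and SAP 12.1.3 take all vaccinated subjects. A sheet-based N would drop a subject who had an unsolicited event but returned no sheet. Template 22 already has a suitable model: subjects given the corresponding dose for each dose row, and subjects given at least one dose for overall/subject.

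**The case against.** The strongest reply is that the operative rule is already in the text: SAP 12.1.3 and protocol 10.5.1 exclude undocumented doses, and a program that follows them produces no dilution. The disputed phrase sits in the column on table terminology rather than the column on deriving percentages. The Co-Ad Dose 3 row is so implausible that the footnote looks like shorthand. SAP 13 calls the template footnotes illustrative and allows minor changes without an amendment. Safety is descriptive, Template 16 prints N on every row, and Template 15 reports sheet compliance by dose, so any dilution would be visible.

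Much of this stands. It makes the bias conditional and its consequences limited. It does not remove the conflict. The 12.1.3 table is SAP text, not a mock, and its derivation column is not dose-specific either. The Template 16 definition has been carried through all four SAP versions, including Amendment 3, which edited templates. A programmer is left with two incompatible instructions.

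A reader might also infer a spurious difference between arms, because the second HZ/su dose is study Dose 2 in Co-Ad and study Dose 3 in Control. The mechanism exists, but the documents give no documentation rate by dose or arm, so neither the size nor the presence of such a difference can be claimed. Nor do they support saying that the report would generally show two percentages for the same event; that risk is clear only for oral temperature.

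**Conclusion.** The denominator rule is inconsistent and should be corrected. If the broad definition were programmed literally, Dose 2 and Dose 3 rates in Templates 16 and 19 would shrink by the factor n_k / N_any. The error is zero when every later sheet is present. On an assumed 2% to 10% missing, it takes a true 60% down by 1.2 to 6.0 percentage points.

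A reader might conclude that the SAP as written does understate later-dose reactogenicity. The documents do not support that without two conditions: that the table and footnotes are followed in preference to the exclusion rule, and that later sheets are in fact missing.

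The individual solicited event rates in Templates 17, 18, 26 and 27 already use the dose-specific N. No confirmatory objective, significance level or sample size is touched.

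**What to change.** - In the SAP 12.1.3 table, Template 19 and the solicited-only version of Template 16, define N for each dose row as subjects for whom that dose is documented, and tie the numerator to events following that dose.
- In the solicited-and-unsolicited version of Template 16, define N for each dose row as subjects who were given that dose, as Template 22 does.
- Keep the any-dose definition for overall/subject rows only: any documented dose in the solicited-only version, any administered dose in the combined version.
- Print no Dose 3 row for Co-Ad.

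The cost is a correction to one SAP table and two template footnotes, with Template 16 split into its two uses. No new data are needed. SAP 13 allows the footnote edits without an amendment; the 12.1.3 table is SAP text and should be corrected there.
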